### 5.4.3. Gastrointestinal Events

Isolated cases of gastrointestinal inflammation (eg, stomatitis, colitis, cecitis) have been noted in subjects receiving idelalisib. Rare cases of gastrointestinal perforation have occurred, generally in the setting of occult carcinoma, mesenteric embolus or diverticular disease. Study treatment (idelalisib) **must** be discontinued in subjects who experience bowel perforation.

Cholangitis manifest as hyperbilirubinemia out of proportion to serum transaminase elevations has been observed. While disease-related factors, neutropenia, toxicity from prior therapies, effects of ongoing supportive care, or pre-existing cholelithiasis may have initiated such events, it is possible that idelalisib played a contributory role. In such subjects, rechallenge with idelalisib has been possible and has not been associated with other severe adverse events. Subjects who have developed evidence of enteritis during idelalisib therapy have been successfully treated with antidiarrheals (eg, loperamide) and with enteric steroidal (eg, budesonide) or non-steroidal (eg sulfasalazine [[Azulfidine®](#)]) anti-inflammatory agents and have been able to continue or resume idelalisib.

For study subjects who develop severe abdominal pain the possibility of a bowel obstruction or perforation should be considered. Appropriate clinical and radiographic examination should be performed and supportive care or surgical intervention should be considered. Upon recovery, ofatumumab may be resumed.

For subjects who develop persistent diarrhea, causes related to concomitant medications or gastrointestinal infections such as *Clostridium difficile* (particularly for patients recently treated with broad spectrum antibiotics), *Shigella*, *Campylobacter*, *Yersinia* and CMV should be considered and treated if appropriate. Depending upon the clinical circumstances, endoscopy and biopsy, with bacterial and viral IHC staining should be considered. In the event that an infectious

cause is not identified, an antimotility agent (eg, loperamide) may lessen symptoms and intervention with enteric steroidal (eg, budesonide) or non-steroidal (eg, sulfasalazine) anti-inflammatory agents should be considered. In such subjects, rechallenge with idelalisib at a lower dose level has resulted in recurrence of symptoms in some but not all subjects and has not been associated with other severe adverse events.

[figure not shown]
Upon recovery and depending upon the type and severity of the initial gastrointestinal event, idelalisib therapy may be continued or resumed and ofatumumab administration may be completed if continued drug administration offers the potential for clinical benefit.

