Grade 4 neutropenia (or occurrence of neutropenic fever or infection)	Interrupt idelalisib. Blood counts must be monitored at least weekly until ANC <math>\leq</math> Grade 2, at which point idelalisib dosing may be resumed at lower dose level.	Delay ofatumumab until Grade $\leq 3$ (ANC $\geq 0.5 \times 10^9/L$ ) and/or neutropenic fever or infection is resolved; thereafter, resume at full dose. Consider G-CSF support to avoid delays. If delay is $> 4$ weeks, discontinue ofatumumab.
Thrombocytopenia		
Grade $\leq 3$	Maintain current dose level and schedule.	Maintain current dose level and schedule.
Grade 4	During combination therapy period, maintain current idelalisib dose level. During continuing therapy period, withhold idelalisib for bruising or bleeding until Grade <math>\leq 3</math>. May resume idelalisib at same or reduced dose level at investigator discretion.	Delay ofatumumab until Grade $\leq 3$ (platelets $\geq 25 \times 10^9/L$ ); thereafter, resume at full dose. If delay is $> 4$ weeks, discontinue ofatumumab.
NON-HEMATOLOGICAL ADVERSE EVENTS		
Cutaneous		
Grade $\leq 1$	Maintain current dose level and schedule.	Maintain current dose level and schedule.
Grade 2	Maintain current dose level and schedule.	Delay ofatumumab until Grade $\leq 1$ ; thereafter, resume at full dose.

NCI CTCAE Grade	Recommendations and Required Action (in italics)	
	Idelalisib	Ofatumumab
Grade 3 or 4	Withhold idelalisib until Grade ≤ 1. May resume at lower dose level or discontinue idelalisib at investigator discretion.	Delay ofatumumab until Grade ≤ 1; thereafter, may resume at full dose or discontinue ofatumumab at investigator discretion.
Stevens-Johnson Syndrome/Toxic Epidermal Necrolysis		
Any Grade	Discontinue idelalisib. Interrupt coadministered medications potentially associated with SJS or TEN. Institute treatment per institutional standards.	
Gastrointestinal Inflammation/Diarrhea		
Grade ≤1	Provide anti-diarrheal agent (eg, loperamide) and maintain current idelalisib dose level and schedule. Obtain history and perform physical exam as outlined in Section 5.4.3.2	Maintain current dose level and schedule.

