### 5.4.2. Dermatological Events

Subjects receiving idelalisib with  $\geq$  Grade 3 rash have generally presented with a maculopapular rash on the trunk and extremities that is occasionally associated with fever and/or pruritus and responded to treatment with diphenhydramine and/or topical or oral corticosteroids.

For subjects who develop a severe rash for which an underlying etiology cannot be identified (e.g., infection, co-suspect drug), study drug *must* be interrupted. Once rash resolves to Grade <1 idelalisib can be resumed at a lower dose level or discontinued at the investigator’s discretion.

Severe cutaneous reactions, including fatal events of Stevens-Johnson syndrome (SJS) and toxic epidermal necrolysis (TEN), have been reported in subjects receiving idelalisib. Assessment of potential causal association between idelalisib and the occurrence of SJS or TEN

has been confounded by the coadministration of antineoplastic agents (e.g., bendamustine, rituximab) and/or other concomitant medications known to be associated with SJS or TEN (e.g., allopurinol). If SJS or TEN is suspected, idelalisib and all coadministered medications associated with SJS or TEN should be interrupted and the subject treated accordingly.

Subjects should be monitored for the development of SJS, TEN, or other severe cutaneous reactions and idelalisib treatment **must** be discontinued if such events occur.

Severe dermatological reactions can occur in patients receiving ofatumumab, most commonly as manifestations of an infusion reaction. Dermatological adverse events have included macular rash, vesicular rash, urticaria, and hyperhidrosis {[Glaxo Group Limited 2011](#)}.

In the case of the occurrence of mucocutaneous reactions during ofatumumab infusion, the recommendations for the management of infusion toxicity (see Section 5.3.3.3) should be followed. The safety of readministration of ofatumumab to patients with other types of severe mucocutaneous reactions has not been determined; thus, for subjects experiencing a Grade  $\geq 3$  non-infusion-related ofatumumab mucocutaneous reaction, consideration should be given to discontinuation of ofatumumab.

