#### **5.7. Duration of Study Drug**

Subjects may continue receiving idelalisib until the occurrence of any events requiring study drug discontinuation as defined in Section 5.8.

Subjects may continue to receive ofatumumab until the earliest of a maximum of 12 infusions or the occurrence of any events requiring study drug discontinuation as defined in Section 5.8.

***Note: Subjects in Arm A will continue receiving idelalisib or ofatumumab, even if the other drug must be discontinued due to toxicity.***

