#### **5.8. Discontinuation of Study Drug**

All study participants may receive idelalisib indefinitely and may receive ofatumumab through 12 infusions. However:

- Any subject has the right to discontinue study drug at any time.
- Any subject who has objective evidence of definitive CLL progression (confirmed by IRC) will discontinue study drug.
- Any subject unable to tolerate a second rechallenge with protocol-described, dose-modified idelalisib at Dose Level –1 (100 mg BID) (see Section 5.3.4) should discontinue idelalisib.
- Any subject who becomes pregnant or begins breastfeeding should discontinue study drug.
- Any subject who becomes significantly noncompliant with study drug administration, study procedures, or study requirements should discontinue study drug.
- The investigator may discontinue study drug, if it is not in the subject's best interest to continue.
- Any subject who is diagnosed with any grade of SJS, TEN, PJP, or organizing pneumonia, or any subject diagnosed with Grade  $\geq 2$  pneumonitis should discontinue study drug.
- Any subject whose benefit-risk profile is not deemed positive by the investigator should discontinue study drug.

If allowed by local regulations, Gilead Sciences may transition subjects from study drug to commercial drug supply when idelalisib becomes commercially available in the country where the subject is living.

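### Section 5.4.2 requires idelalisib to stop for severe skin reactions other than SJS/TEN, but Table 5-4 allows lower-dose rechallenge; Section 5.8 omits both this stop and the bowel perforation stop

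*Protocol*

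**What the plan says.** **Where stopping is defined.** Section 5.7 says: "Subjects may continue receiving idelalisib until the occurrence of any events requiring study drug discontinuation as defined in Section 5.8". Section 5.8 then gives a bulleted list. Its event-specific toxicity bullet begins "Any subject who is diagnosed with any grade of SJS, TEN, PJP, or organizing pneumonia" and goes on to Grade ≥2 pneumonitis. Other bullets cover pregnancy or breastfeeding and failure of a second rechallenge at 100 mg BID. There are also judgment bullets, among them: "Any subject whose benefit-risk profile is not deemed positive by the investigator should discontinue study drug".

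**Skin events.** Section 5.4.2 asks sites to watch for "SJS, TEN, or other severe cutaneous reactions and idelalisib treatment"; the sentence goes on to make stopping mandatory. Earlier in the same section, a severe rash with no identified cause calls for interruption, after which "idelalisib can be resumed at a lower dose level" or stopped, as the investigator decides. Table 5-4 has one row for SJS/TEN (discontinue) and a separate Cutaneous row. For Grade 3 or 4 the Cutaneous row gives "Withhold idelalisib until Grade ≤ 1" as the required action, followed by: "May resume at lower dose level or discontinue idelalisib at investigator discretion".

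**Perforation.** Section 5.4.3 says idelalisib must be "discontinued in subjects who experience bowel perforation". Neither Section 5.8 nor Table 5-4 names the event.

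**The concern.** Section 5.3.4 tells sites that the marked actions in Table 5-4 are compulsory, and Section 5.7 sends them to Section 5.8 for the events that end treatment. A site that follows 5.3.4, Table 5-4, 5.7 and 5.8 closely meets no named mandatory stop for a severe skin reaction that is not SJS or TEN. What it meets is an instruction to withhold and an option to restart at the lower dose. Section 5.4.2 tells the same site to stop for good reason: the protocol reports fatal SJS and TEN in subjects receiving idelalisib. At stake is rechallenge of a subject whom another part of the protocol says must come off the drug.

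For perforation the worry is narrower. A reader who relies on 5.8 alone will not find a stop that 5.4.3 makes compulsory.

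**Working it through.** There is no figure to recompute. The check is to take each idelalisib discontinuation that Section 5.4 words as a must and look for it in Section 5.8 and Table 5-4.

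| Event | Section 5.4 | Section 5.8 | Table 5-4 |
|---|---|---|---|
| SJS or TEN | must stop (5.4.2) | named | discontinue row |
| Other severe skin reaction | must stop (5.4.2) | not named | no discontinue row; Grade 3 or 4 goes to Cutaneous row: withhold, may resume lower |
| Bowel perforation | must stop (5.4.3) | not named | no row of its own |
| Grade ≥2 pneumonitis | must stop (5.4.9) | named | discontinue row |
| Pregnancy or breastfeeding | must stop (5.4.11) | named | not a table event |

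Two stops are missing from 5.8, and they differ in kind.

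**Skin reaction.** Suppose a subject has a Grade 4 skin reaction that is not SJS or TEN.

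- Under 5.4.2, idelalisib is discontinued.
- Under Table 5-4, idelalisib is withheld until Grade ≤1 (required) and may then restart at 100 mg BID (optional).
- Under 5.7 and 5.8, no named event applies, and only the judgment bullets remain.

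The Cutaneous row is headed by organ system and is not limited to rash, so it covers this reaction. Section 5.4.2 does suggest a distinction: it treats severe rash first, then introduces severe cutaneous reactions by reference to SJS and TEN. It sets no grade or clinical feature that marks the boundary, and Table 5-4 does not carry the distinction over.

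**Perforation.** Two texts could be set against the 5.4.3 stop.

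- The closing sentence of 5.4.3 lets idelalisib continue or resume after a gastrointestinal event. It makes this depend on the type and severity of the event, so it leaves room for an event type that bars resumption.
- The residual row of Table 5-4 for other nonhematological events of Grade ≥3 offers resumption or discontinuation. The table covers treatment-related events, and under 5.3.4 text not marked as required is a guideline.

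The 5.4.3 paragraph on suspected obstruction or perforation names only ofatumumab for resumption, which fits a permanent idelalisib stop. None of this contradicts the stop. What remains is its absence from 5.8.

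**The case against.** The best defence is that Section 5.4 is the part of the protocol devoted to event-specific stops, that its compulsory wording is never cancelled, and that Section 5.8 does not call itself complete. Section 5.8 also leaves out PML (5.4.8), AML (5.4.1), HBV reactivation for ofatumumab (5.4.5) and the required stop for Grade 4 bilirubin in Table 5-4, so it is evidently not a full register. On skin events, a site that discontinues complies with both 5.4.2 and Table 5-4, because the table offers discontinuation as an alternative. Read in context, the 5.4.2 stop concerns reactions of the SJS/TEN class. There are safeguards as well: idelalisib dose changes should where possible be discussed with the medical monitor beforehand, and a dose reduction has to be entered in the IWRS.

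Much of this stands. It disposes of a stronger reading that a reader might infer, namely that the protocol allows idelalisib rechallenge after bowel perforation. A compulsory, event-specific stop is not displaced by a conditional sentence and a residual guideline row. It also rules out saying that nothing separates severe rash from the other reactions, since 5.4.2 gives a contextual cue.

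It does not remove the skin conflict. That one course satisfies both texts does not help when the table expressly offers a second course that 5.4.2 forbids. No sentence says which text prevails. Section 5.4 is itself headed as recommendations, while 5.3.4 presents the marked Table 5-4 actions as binding. The 5.8 judgment bullets are discretionary and cannot stand in for a compulsory stop.

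**Conclusion.** The point holds in two parts of unequal weight. For severe skin reactions other than SJS/TEN there is a real conflict: 5.4.2 requires discontinuation, while Table 5-4 requires only withholding and permits a lower-dose restart. For bowel perforation there is an omission from the list that 5.7 treats as defining; the stop itself is clear and in force in 5.4.3.

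The size is two compulsory stops absent from 5.8, one of which also meets a conflicting table row. A percentage of omitted rules would add nothing, because it depends on whether the 5.4.2 sentence is counted as one rule or two. About 170 planned Arm A subjects are treated under these rules. The protocol gives no expected number for either event and calls perforation rare, so no count of affected subjects can be derived. Sample size, power, alpha and endpoint definitions are untouched.

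The conclusion assumes that a Grade 3 or 4 skin event outside SJS/TEN is read into the Cutaneous row, as its heading implies. It should be corrected on safety grounds.

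**What to change.** - In Table 5-4, limit the resume text of the Cutaneous Grade 3 or 4 row to rash.
- Extend the SJS/TEN discontinue row, and the corresponding Section 5.8 bullet, to other severe cutaneous reactions of that type.
- Add bowel perforation to Section 5.8 as an idelalisib stop.
- State in Sections 5.7 and 5.8 that the discontinuation rules in Section 5.4 apply and take precedence over any wording that allows resumption. This sentence also covers AML, PML and HBV reactivation, which 5.4 states clearly and which lack only a cross-reference.

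The cost is a wording amendment: two table rows, two edits to the 5.8 list and a precedence sentence. It adds no visit, procedure or data collection and leaves the statistical design unchanged.

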#### 5.4.3.1. Investigation for Idelalisib Late Onset or Severe Diarrhea/Colitis

See CTCAE Version 4.03 for definitions of colitis and diarrhea.

Among idelalisib-treated patients who reported diarrhea or colitis, the median time to onset of any grade diarrhea or colitis was 1.9 months (range, 0.0–29.8), of grade 1 or 2 was 1.5 months (range, 0.0–15.2) and of grade 3 or 4 was 7.1 months (range, 0.5–29.8). Kaplan–Meier curves of time to onset of diarrhea or colitis are shown for all idelalisib- treated patients in [Figure 5-1](#)

**Figure 5-1. Kaplan-Meier Time to Diarrhea or Colitis**

Idelalisib-associated severe diarrhea responds poorly to antimotility agents however, median time to resolution ranged between 1 week and 1 month across trials following interruption of idelalisib treatment and, in some instances, initiation of corticosteroid treatment {[Gilead Sciences Inc 2014](#)}.

#### 5.4.3.2. Evaluation for Gastrointestinal Events/Colitis

For any grade diarrhea or colitis the following is *required*. Obtain history of onset and duration of diarrhea, including description of number of stools and stool composition (eg, watery, bloody, nocturnal), travel history, dietary changes and a medication review to identify possible diarrheogenic agents. Perform physical examination including assessment for fever, dizziness, abdominal pain/cramping, and weakness (ie, evaluate for sepsis, bowel obstruction, dehydration).

For Grade  $\geq 2$  colitis and diarrhea (unless clinical diagnosis is established from medical history and physical examination), the following testing is **required**:

- Stool culture for routine pathogens (Salmonella, Shigella, Campylobacter species), testing for Clostridium difficile toxin, Rotavirus, Cytomegalovirus (CMV), and Adenovirus.
- Stool for Ova and Parasites (Cryptosporidium parvum, Isospora belli, Enterocytozoon bieneusi, Septata intestinalis, Strongyloides, Microsporidia, Entamoeba histolytica, Cyclospora), Giardia antigen.

For Grade  $\geq 3$  or persistent Grade 2 colitis or diarrhea, without clear etiology (eg, clostridium difficile enterocolitis), endoscopy with biopsy is strongly recommended. All biopsy samples should include immunohistochemistry (IHC) and PCR for CMV, Adenovirus.

CCI

#### 5.4.3.3. Differentiation Between Small-bowel and Large-bowel Diarrhea

Differentiation between small-bowel and large-bowel diarrhea: maybe possible on a clinical basis. If unclear, consider upper and lower tract endoscopy with biopsy.

- Small bowel diarrhea is characterized by large volume diarrhea (more than one per day), and is possibly associated dehydration weight loss and paraumbilical pain. Consider an endoscopic small-bowel biopsy and evaluate other etiologies such as celiac disease.
- Large-bowel diarrhea may present with lower pelvic pain, tenesmus, generally smaller stool volumes with gross blood frequently found in the stool; consider a colonoscopic evaluation and biopsy.

#### 5.4.4. Hematological and Immunological Events

In the Phase 1 experience with idelalisib in CLL, patients with Grade  $\geq 3$  neutropenia, anemia, and/or thrombocytopenia were enrolled to clinical trials. Decreased levels of neutrophil counts, hemoglobin, or platelet counts during therapy were largely due to minor fluctuations in these parameters among patients with pre-existing hematological abnormalities due to disease or prior therapy. Thus, idelalisib did not appear to induce overt myelosuppression. Obvious patterns of drug-mediated reductions in circulating CD4+ lymphocyte counts or suppression of serum IgG levels were also not observed.

Treatment-emergent Grade 3 or 4 neutropenia events, including febrile neutropenia, have occurred in subjects treated with idelalisib. All subjects should have their blood counts monitored at least every 2 weeks for the first 6 months of idelalisib treatment. For subjects who develop ANC 0.5 to  $< 1.0$  Gi/L, blood counts must be monitored weekly. For subjects who develop ANC  $< 0.5$  Gi/L, idelalisib must be interrupted and blood counts monitored weekly until ANC is  $\geq 0.5$  Gi/L, at which point, idelalisib dosing may be resumed at 100 mg BID. Neutropenia should be managed according to established clinical guidelines.

Prolonged ( $\geq 1$  week) severe neutropenia can occur with ofatumumab. Of 108 patients with normal neutrophil counts at baseline in the Phase 2 pivotal clinical trial experience {Wierda 2010}, 45 (42%) developed Grade  $\geq 3$  neutropenia and 19 (18%) developed Grade 4 neutropenia. Some patients experienced new onset Grade 4 neutropenia of  $> 2$  weeks in duration {Glaxo Group Limited 2011}. Suppression of mean serum IgG and IgA levels has not been seen. Anemia and thrombocytopenia are not as prominent.

Because idelalisib is not associated with substantial myelotoxicity, alterations in idelalisib therapy for such events during combination idelalisib/ofatumumab therapy should be avoided, if possible. Dose modifications during combination idelalisib/ofatumumab therapy (Arm A) or during single-agent ofatumumab therapy (Arm B) should focus on alterations in ofatumumab scheduling; in subjects with persistent neutropenia despite G-CSF administration, ofatumumab doses may be delayed for as long as 4 weeks to allow recovery of neutrophil counts to Grade  $\leq 3$  (see Table 5-4). At the conclusion of combination therapy, subjects with protracted or symptomatic neutropenia or thrombocytopenia during continuing single-agent idelalisib therapy may warrant a study drug dose modification if myelosuppression is unresponsive to G-CSF supportive care or is symptomatic. No modification of either drug for changes in circulating CD4+ counts or Ig levels is planned.

